4 STUDY DESIGN

4.1 General Description

This multicenter, open-label study, will evaluate the pharmacokinetics, safety, tolerability, and the exploratory efficacy of MM36 1% ointment when applied twice daily for up to 4 weeks in subjects 2 to < 18 years of age with atopic dermatitis, at the upper range of disease severity. This study will also evaluate the systemic availability of MM36 1% when applied topically under maximal use conditions.

Following screening (within 30 days prior to the first dose of study drug) and confirmation of study qualification, subjects will be registered and assigned (V2) to one of three treatment groups based on the subject's age at Screening (V1). The first dose of study drug will be applied in the study clinic (V2/Day 1) and blood samples will be collected for evaluation of PK prior to the first application (0 hours) and at 1 hour (\pm 15 minutes), 4 hours (\pm 30 minutes) and at 8 hours (\pm 1 hour) after application of study drug. On Day 15, the study drug will again be applied in the study clinic, and blood samples will be collected for PK prior to dosing and at 1 hour (\pm 15 minutes), 4 hours (\pm 30 minutes) and at 8 hours (\pm 1 hour) after application of study drug.

Corporate Confidential Information

At Screening (V1) and Baseline (V2), subjects with atopic dermatitis that are 2 to less than 12 years of age (Group 2 and 3) must have a treatable area comprising \geq 35% BSA involvement (excluding scalp and venous access areas), and subjects 12 years of age and older (Group 1) must have \geq 25% BSA involvement (excluding scalp and venous access areas) (i.e., maximal use conditions). The same (or greater, BSA if area involved expands) amount of study drug topically applied at baseline will continue to be applied twice daily, to the same area where study drug was applied on Day 1, even if the % BSA improves over the course of the first 2 weeks (14 days) of treatment. Between Day 15 (after the maximal use application and collection of PK samples) and Day 28, the study drug will only be applied to the involved areas. The last application of study drug will be given the evening before the final visit (V6). Refer to [Figure 1](#).

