6.9 Selected Treatment Area and BSA% to be Treated

6.9.1 Maximal Use Treatment Area

The selected treatment area is defined as the collective areas selected for treatment in the study and it must be identified by the Investigator. At Baseline (V2) subjects 2 to less than 12 years of age must have BSA% involvement (affected area) of $\geq 35\%$ (excluding scalp and venous access areas) and subjects ≥ 12 years of age must have a BSA% involvement of $\geq 25\%$ BSA% (excluding scalp and venous access areas). Once the selected treatment area is set at Baseline, it may increase in area during the duration of the study (for expanded disease), but will not decrease in area during the first 2 weeks (14 days) of treatment (through collection of the Day 15 PK samples).

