6.9.2 Treatment for Improvement in Selected Treatment Area

In order to assess the pharmacokinetic profile of MM36 1% (w/w) under maximal use conditions, all originally involved BSA treated with study drug at Baseline will continue to be treated with MM36 1% ointment even if the area has cleared until after the PK samples have been collected on Day 15. On Day 15, the proportion of the treatment area will be defined as either involved or normal (cleared) skin and will be recorded in the source and eCRF.

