7.2 Baseline (Visit 2/Day 1)

It is estimated that this visit will take approximately 8 hours to complete. Following verification of study eligibility (meets all inclusion and none of the exclusion criteria), the subject will be registered in the study.

- Interview
 - Review and record prior medications (those taken since the last visit);
 - Evaluate Inclusion/Exclusion Criteria (update);
 - Update AEs since last visit;
 -
- Assessments Prior to First Application
 - Measure and record weight;
 - Obtain and record vital signs;
 - Perform a 12-Lead ECG;
 - Perform a complete physical examination;
 - Assess BSA for affected AD and record on body grid;
 -
 -
- Sample Collection
 - Prior to first application:
 - Collect blood samples for safety laboratory testing and PK; and
 - Collect urine sample for urine pregnancy testing (as applicable).
 - Post application:

- Collect a blood sample for PK at 1 hour (\pm 15 minutes), 4 hours (\pm 30 minutes) and 8 hours (\pm 1 hour) post application.
- Instructions
 - Dosing and Application Training
 - Based on the BSA involved, the appropriate number of tubes of study drug will be dispensed along with a scale and dosing cups.
 - The parent/guardian (caregiver) and/or subject will be trained by the study site personnel on measuring and applying the study drug and recording the information in the electronic dosing diary.
 - The parent/guardian (caregiver) or subject will apply the study drug to the affected areas twice daily (approximately 12 hours apart).
- Corporate Confidential Information

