7.3 Visit 3/Day 8 (\pm 1)

It is estimated that this visit will take approximately 1.5 hours to complete.

- Interview
 - Update medications (those taken since the last visit);
 - Assess for AEs; and
 - Corporate Confidential Information
- Assessments
 - Assess application sites;
 - Perform abbreviated physical exam (only as applicable for evaluation of AEs);
 - Obtain and record vital signs;
 - Assess BSA for affected AD and record on body grid;
 - Corporate Confidential Information
 - Photograph AD sites as applicable; and
 - Compliance check (weight check of study drug and review diary completion).

- Instructions
 - Dispense study drug;
 - Review dosing procedure and have the parent/guardian (caregiver)/subject apply the study drug to the affected areas; and
 - Schedule Return visit for 1 week (Day 15) and remind parent/guardian (caregiver) not to apply study drug in the morning before the visit and to bring all used and unused study drug to next visit.

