8.4 Dosing

The subject (parent/guardian (caregiver) will be instructed on proper application of the study drug and will apply the initial application on Day 1 at the study site. The proper dose dispensing procedure and use of the study drug will be demonstrated and observed by study staff to ensure subject (parent/guardian (caregiver) understand the instructions.

- For each dosing period, the subject, under the supervision of the parent/guardian (caregiver), or the parent/guardian (caregiver), will dispense the required amount of ointment (by weight) using the measuring cup(s) provided.
- The subject should wash his/her hands both before and after applying study ointment. If applied by the parent/guardian (caregiver), they should also wash hands before and after applying study ointment, but will also wear non-latex gloves (provided by the Sponsor).
- The subject (parent/guardian (caregiver) will apply a thin layer of ointment to affected areas twice daily (approximately 12 hours apart) for 28 consecutive days.
- It is recommended that the ointment be applied after showering/bathing. The skin should be dry prior to application. Important: Subjects should not swim or bathe or wipe application area for a minimum of 20 minutes after application of ointment.
- The ointment should be rubbed in gently and completely, avoiding contact with the eyes.
- Subject's (parent/guardian (caregiver) will be instructed not to administer the study drug in the morning on the day of the study visit to avoid any effect of the study drug on the assessments.
- An adult (≥ 18 years of age) parent/guardian (caregiver) will verify if the study drug was weighed appropriately and applied as directed. Application details will be recorded in the electronic diary.

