4. STUDY DESIGN

4.1 Overall Study Design

This multicenter, open-label study, will evaluate the pharmacokinetics, safety, tolerability, and the exploratory efficacy of MM36 1% ointment when applied twice daily for up to 4 weeks in subjects 2 to < 18 years of age with atopic dermatitis, at the upper range of disease severity. This study will also evaluate the systemic availability of MM36 1% when applied topically under maximal use conditions.

Approximately 45 subjects will be registered for an estimated 32 completed subjects. Following screening (within 30 days prior to the first dose of study drug) and confirmation of study qualification, subjects will be registered and assigned (Day 1) to one of three groups based on the subject's age at Screening. The first dose of study drug will be applied in the study clinic (Day 1) and blood samples will be collected for evaluation of pharmacokinetics (PK) prior to the first application (0 hours) and at 1 hour (\pm 15 minutes), 4 hours (\pm 30 minutes) and at 8 hours (\pm 1 hour) after application of study drug. On Day 15, the study drug will again be applied in the study clinic, and blood samples will be collected for PK prior to dosing and at 1 hour (\pm 15 minutes), 4 hours (\pm 30 minutes) and at 8 hours (\pm 1 hour) after application of study drug.

Corporate Confidential Information

At Screening and Baseline (Day 1), subjects with atopic dermatitis that are 2 to less than 12 years of age (Group 2 and 3) must have a treatable area comprising \geq 35% BSA involvement

(excluding scalp and venous access areas), and subjects 12 years of age and older (Group 1) must have $\geq 25\%$ BSA involvement (excluding scalp and venous access areas) (i.e., maximal use conditions). The same (or greater, BSA if area involved expands) amount of study drug topically applied at baseline will continue to be applied twice daily, to the same area where study drug was applied on Day 1, even if the % BSA improves over the course of the first 2 weeks (14 days) of treatment. Between Day 15 (after the maximal use application and collection of PK samples) and Day 28, the study drug will only be applied to the involved areas. The last application of study drug will be given the evening before the final visit (Day 29).

The maximum individual study participation is approximately 60 days (screening (Day -30) through final Day 29 (± 1 day) Visit).

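### Protocol 7.2, 7.3, 7.4, 8.4 and Appendix A direct ointment to affected areas, while 4.1, 6.9 and SAP 4.1 require the full Day 1 area, cleared skin included, through the last Day 15 PK sample

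*Protocol*

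**What the plan says.** The area rule is in the protocol synopsis, Protocol 4.1 and 6.9, and SAP 4.1. For the first two weeks the same or a greater amount of drug goes "to the same area where study drug was applied on Day 1, even if the % BSA improves" (SAP 4.1; Protocol 4.1 agrees). Section 6.9.1 lets the selected treatment area grow with the disease, but it "will not decrease in area during the first 2 weeks (14 days) of treatment (through collection of the Day 15 PK samples"). Section 6.9.2 deals with healing directly: the area treated at Baseline stays under treatment "even if the area has cleared until after the PK samples have been collected on Day 15". Between then and Day 28, Protocol 4.1 says "the study drug will only be applied to the involved areas".

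The sections that staff and families work from name a different area:

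- **8.4 Dosing:** the subject or caregiver "will apply a thin layer of ointment to affected areas twice daily (approximately 12 hours apart) for 28 consecutive days".
- **7.2 (Day 1), home-dosing bullet:** the caregiver or subject "will apply the study drug to the affected areas twice daily (approximately 12 hours apart").
- **7.3 (Day 8):** staff are to review dosing and "have the parent/guardian (caregiver)/subject apply the study drug to the affected areas".
- **7.4 (Day 15, the PK dose):** the same instruction as 7.3.
- **Appendix A:** a stated number of grams goes on the affected areas that the doctor has marked, twice daily for 4 weeks.

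None of these five mentions cleared skin, a change after the Day 15 samples, or Section 6.9.

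**The concern.** In this protocol, *affected* is a word for current disease. Section 6.8 uses it for active atopic dermatitis whose extent may rise or fall during the study. The assessment lists in 7.3 and 7.4 use it the same way when they ask for the BSA of affected AD. A reader of 7.3, 7.4 or 8.4 alone would therefore take affected areas to mean skin that is diseased today, and would leave out skin that has cleared.

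The Schedule of Activities sends sites to 8.4 for caregiver training, observed application, dosing and diary. It does not send them to 6.9 for any of these.

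At stake is the Day 15 half of the primary endpoint: plasma concentrations of MM36 and its metabolites after two weeks of twice-daily use. The study exists to measure exposure under maximal use. If cleared skin is dropped before or at the Day 15 dose, those samples describe a smaller treated area than the design intends.

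**Working it through.** **1. The texts side by side**

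| Place | Area to treat | Cleared skin kept? | Change after Day 15 samples? |
|---|---|---|---|
| Synopsis, Protocol 4.1, SAP 4.1 | Day 1 area, or more | Yes | Yes, involved areas only |
| 6.9.1 | Selected treatment area; may grow, not shrink | Implied | Restriction ends there |
| 6.9.2 | All area treated at Baseline | Yes, explicit | Restriction ends there |
| 7.2 home dosing | Affected | Silent | Silent |
| 7.3 (Day 8) | Affected | Silent | Silent |
| 7.4 (Day 15) | Affected | Silent | Silent |
| 8.4 | Affected, 28 days | Silent | Silent |
| Appendix A | Affected, as marked, 4 weeks | Silent | Silent |

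On Day 1 itself the two areas coincide. They part as soon as any treated skin clears. Section 7.4 matters most, because the PK dose belongs on the full area and home dosing narrows after the last sample; it states neither.

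**2. How many applications each rule covers**

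Inputs: twice daily; 28 days (8.4); visits ±1 day (Schedule of Activities); visit-day morning dose given in clinic; last dose the evening before Visit 6. The 8-hour sample precedes the evening dose, which is about 12 hours after the clinic dose.

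- Total: 28 × 2 = 56. With Visit 6 on Day 28 to 30, 54 to 58. The upper figure matches the cap of 58 in SAP 7.9.9.1.
- Full-area applications = 2 × (PK visit day − 1) + 1. Day 14: 27. Day 15: 29. Day 16: 31.
- Involved-only applications: nominally 56 − 29 = 27. Across both windows, from 54 − 31 = 23 to 58 − 27 = 31.
- Full-area applications from the Visit 3 clinic dose through the PK dose = 2 × (PK visit day − Visit 3 day) + 1. Nominal: 2 × (15 − 8) + 1 = 15. Range: 2 × (14 − 9) + 1 = 11 to 2 × (16 − 7) + 1 = 19.

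These count applications given under unclear wording. They do not count errors.

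**3. What a literal reading would do to the treated area (illustration)**

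The 8.3 formula is grams = overall BSA × treated fraction × 10 g/m². It reproduces the protocol's example: 0.7 × 0.32 × 10 = 2.24 g.

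The documents give no clearing rate, so 25%, 50% and 75% of the Day 1 area cleared by Day 15 are assumptions. BSA values are from the table in 6.7; involvement is at the eligibility minimum.

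| Subject | Day 1 | 25% cleared | 50% cleared | 75% cleared |
|---|---|---|---|---|
| Age 6, 0.8 m², treated BSA | 35% | 26.25% | 17.5% | 8.75% |
| Same, grams if scaled to area | 2.80 | 2.10 | 1.40 | 0.70 |
| Age 14–17, 1.6 m², treated BSA | 25% | 18.75% | 12.5% | 6.25% |
| Same, grams if scaled to area | 4.00 | 3.00 | 2.00 | 1.00 |

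For a subject enrolled at the minimum, dropping any cleared skin takes the treated area below the protocol's maximal-use threshold.

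The gram rows apply only if the amount is scaled down too, which 4.1 forbids. If grams are held, the same dose goes on less skin: at age 6 with half cleared, 2.80 ÷ (0.8 × 0.175) = 20 g/m² instead of 10. Fixed grams therefore do not fix the area.

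**The case against.** The strongest reply is that the rule is not missing. The synopsis, 4.1, 6.9 and SAP 4.1 agree, 6.9.2 addresses cleared skin expressly, and a specific provision should control over a general how-to list. Nor are caregivers left to choose the area by eye:

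- Appendix A ties the area to a doctor-marked diagram with prescribed grams and an acceptable range. Before Day 15 the only stated trigger for a new diagram is worsening (6.9.3), so the default keeps the Day 1 area.
- Section 8.4 itself asks an adult to verify that drug was weighed and applied as directed.
- Section 8.5 has amount and location entered in the diary at each application, and returned tubes are weighed.
- The Day 15 PK dose is given in clinic, where 6.9.2 requires that "the proportion of the treatment area will be defined as either involved or normal (cleared) skin".

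All of this stands and lowers the risk. It does not remove the conflict. The caregiver sheet still says affected areas for 4 weeks, 7.4 gives the same instruction for the PK dose, and SAP 7.9.9.1 summarises days, applications, compliance and total amount but not location.

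A reader might also infer more than the documents support:

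- **That 7.5 is wrong.** It is not. At Day 22 only involved skin is treated, so affected areas is correct there.
- **That the 8.3 dosing module will cut the dose as skin clears.** The field is named for involvement, but Step 1 refers to areas that will be treated and the synopsis to the intended treatment area. The stated output is a number of tubes, and the example rounds 1.16 up to 2.
- **That having no stated narrowing diagram after Day 15 threatens the primary endpoint.** It could only lead to over-treatment after PK sampling has ended.

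One limit of this check is that 7.2 has a redacted bullet under Instructions and the Appendix A diagram is not visible. The blank bullets in 7.4 fall under Interview and Assessments, so redaction does not account for the silence in its Instructions.

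**Conclusion.** Wrong as written, as a minor wording correction. The design is sound and its rule is clearly stated. The fault is that the visit, dosing and caregiver text conflicts with that rule and, followed literally once skin clears, could shrink the treated area before or at the Day 15 PK dose. On the nominal schedule 29 of 56 applications fall under the full-area rule, 15 of them from the Day 8 clinic dose through the PK dose.

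It would be going too far to say that Day 15 exposure will be understated or that the primary endpoint is compromised. That would need skin to clear and the diagram and 6.9 to be disregarded. The documents give no clearing rate, no relation between treated area and plasma concentration, and no comparison of absorption through cleared and active skin. The size of any effect cannot be stated.

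The conclusion rests on reading *affected* as 6.8 and the visit lists use it, and on the visible text only.

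**What to change.** - **7.2 (home-dosing bullet), 7.3, 8.4 and Appendix A:** replace affected areas with *the full selected treatment area set on Day 1 plus any new areas, including skin that has cleared, through the last Day 15 PK sample (Section 6.9); involved areas only thereafter*.
- **7.4:** state that the in-clinic PK dose goes on the full selected treatment area, and that after the 8-hour sample the caregiver receives an updated Appendix A sheet for involved areas only.
- **7.5:** no change.
- **8.3 (optional):** say that the BSA% entered in the dosing module is the area to be treated.

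The cost is a few sentences and one re-issued caregiver sheet at an existing visit. No visits, samples or analyses are added.

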8.5 Compliance

The parent/guardian (caregiver)/subject will record the amount of drug used at each application and application location in the electronic diary. All used and unused study drug will be returned at all protocol-specified visits for study drug inventory and assessment of subject adherence.

The weight of the study drug will be measured before it is dispensed and after it is returned at Visit 3/Week 1, Visit 4/Week 2, Visit 5/Week 3 and Visit 6/Week 4. Each dispensing and return of study drug as well as the weight of study drug will be documented in the eCRF. The dispensing and return of all study drug will be recorded on the study drug dispensing log. The subject number/initials and the initials and date of the person dispensing and receiving the returned medication will be documented on this form.

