8.3 Dispensing

As reported in Nelson et al, 2006, “an average of 9.9 g/m² (equivalent of 1.0 mg/cm²) of a topical agent (by weight) are required by a disciplined operator to achieve a thin, even layer of ointment on a patient” (pp. 224). Therefore, to determine the number of grams (by weight) per day, the Investigator/designee will use the following formula:

Step 1 Formula to Calculate Grams (by weight) of MM36 1% to Use Per Dose:

$$\text{Overall BSA (m}^2\text{)} \times \text{Total (BSA \%)} \text{ of All areas of involvement that will be treated} \times 10 \text{ grams/m}^2 = \text{Grams of ointment per application}$$

Example: A six-year-old boy with 32% BSA involved areas of AD

$$0.7 \text{ m}^2 \times 32\% \text{ (or 0.32)} \times 10 \text{ grams/m}^2 = 2.24 \text{ grams/application}$$

Step 2 Formula to Calculate Grams Needed to Dose BID for 1 Week (7 Days):

$$\text{Grams of ointment needed per Application} \times \text{Number of applications Per day} = \text{Total grams of ointment needed per day} \times \text{Number of Treatment Days} = \text{Total Grams Needed}$$

Example continued:

$$2.24 \text{ grams} \times 2 = 4.48 \text{ grams} \times 7 = 31.36 \text{ grams}$$

Step 3 Formula to Calculate Number of MM36 Tubes of Study Drug (27 grams per each) Needed for 1 Week (7 Days) of Treatment:

$$\text{Total Grams Needed} \div 27 \text{ grams (weight per 1 tube of study drug)} = \text{Number of Tubes to be dispensed}$$

Example continued:

$$31.36 \text{ grams} \div 27 \text{ grams (weight per 1 tube of study drug)} = 1.16 \text{ tubes (dispense 2 tubes)}$$

The table below (Table 4) is provided as general guide to determine the amount of study drug to be dispensed based on a subject's BSA and their intended area of application. Exact calculation will be done on an individual basis. The Investigator or designee will enter the subject's overall BSA, BSA% involvement and intended number of treatments (until the next visit) into the dosing module in the eCRF. The number of tubes to be dispensed will be calculated.

Table 4 Estimated Dispensing Table

Age Range	Estimated ^a BSA m ² Of the Average 50 th Percentile for Males and Females	Approx ^b Grams of Ointment Needed for Application to Every 1% BSA Involvement	Grams (weight) of Ointment Required Per Application to a Minimum Involved Area of 25%	Grams of Ointment Required Per Application to a Minimum Involved Area of 35%
2 - 3	≥ 0.5 to < 0.7	0.07	1.75	2.45
4 - 6	≥ 0.7 to < 1.0	0.10	2.5	3.5

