7 - 11	≥ 1.0 to < 1.3	0.13	3.25	4.55
12 - 13	≥ 1.3 to < 1.6	0.15	3.75	5.25
14 - 17	≥ 1.6 to < 1.9	0.20	5.0	7

^a Kuczmarski et al, 2000

^b Nelson, 2006

The subject/subject's parent/guardian (caregiver) will be provided a calibrated scale and measuring cups to dispense the calculated dose for each application. Procedure will be

discussed with the subject or parent/guardian (caregiver) at the site and documented that proper training occurred prior to first application (refer to [Appendix A](#)).

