APPENDIX A – DOSING INSTRUCTIONS

Apply _____ grams on the affected areas noted below and on the diagram by your doctor:

(Site: Please circle areas affected below and on diagram)

Head/Neck

Trunk

Upper Limbs

Lower Limbs

Acceptable Range for Dosing: _____ to _____

- At each study visit, you/your child will be given enough tubes of study drug until the next visit.
- Be sure to wash your hands before and after applying study drug.
- Using the measuring cups and scale, measure out the amount of ointment to be applied.
- If you squeeze out too much of the ointment in the medicine cup, record the initial weight and scoop off the excess ointment and discard it (throw it away). Reweigh the ointment again to make sure that the dose is within the acceptable range for dosing (bottom of page 1). Please record the details of the change in the chart on the next page.
- Apply the study drug twice daily; once in the morning and once in the evening for 4 weeks.
- If the study drug is applied by a parent/caregiver, they will need to wear the protective gloves provided.
- It is recommended that the ointment be applied after showering/bathing. The skin should be dry. Important: Subjects should not swim or bathe or wipe application area for a minimum of 20 minutes after application of ointment.
- The ointment should be rubbed in gently and completely, avoiding contact with the eyes.
- A parent/caregiver must confirm how much of the study drug was applied and note this on the dosing diary (provided).
- On the morning of a study visit:
 - Do not apply the study drug so that the application areas can be checked by the study doctor/nurse.
 - You/your child will be asked to apply the study drug in the study clinic so that a study team member can see how you are using the study drug.
 - Bring the dosing diary and ALL used and unused tubes of study drug to the clinic.

The Next Study Visit is Scheduled for: _____ at _____

If you accidentally squeezed out too much medication into the cup, please fill out this section.

Please record the weights BEFORE and AFTER you scoop off the extra ointment in the chart below.

Date of Dose	AM/PM Dose	BEFORE weight of study ointment	AFTER weight of study ointment	Discarded by:

Corporate Confidential Information

Corporate Confidential Information

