7.9.9 Safety Analyses

7.9.9.1 Extent of Exposure

The extent of exposure to study drug will be summarized by total number of days of exposure, total number of applications, percent compliance, and total amount of study drug applied. Total number of applications will be determined by the number of entries in the dosing diary. Total number of days of exposure will be computed as follows:

Days of Exposure = Date of Last Application – Date of First Application + 1.

To compute percent compliance, total number of expected applications will be calculated by:

Expected applications = $2 * (\text{Study Completion/Discontinuation Date} - \text{Date of First Application})$.

If the total number of expected applications exceeds 58 then it will be set to 58. Percent compliance will be calculated from total number of applications and total number of expected applications as follows:

Percent Compliance = $100 * (\text{Total Applications}/\text{Expected Applications})$.

Percent compliance will not be calculated for subjects who are lost to follow-up.

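### Compliance is scored by counting applications, although the dose is a weight and grams are recorded, so the tables cannot show whether maximal-use dosing was delivered at home before the Day 15 PK samples

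*Protocol*

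**What the plan says.** **The dose is a weight.** Protocol 8.3 sets grams per application as overall BSA × percentage of BSA treated × 10 g/m². Families "will be provided a calibrated scale and measuring cups to dispense the calculated dose for each application". Under Protocol 8.4 the subject or caregiver "will dispense the required amount of ointment (by weight) using the measuring cup(s) provided". Staff enter overall BSA, "BSA% involvement and intended number of treatments (until the next visit) into the dosing module in the eCRF", so the inputs to the prescribed weight are in the database.

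**Grams are collected, with adherence as a stated purpose.** Protocol 8.5 has the diary record the amount used at each application. Tubes are weighed before dispensing and on return at V3, V4, V5 and V6, and the weights go into the eCRF. The section adds: "All used and unused study drug will be returned at all protocol-specified visits for study drug inventory and assessment of subject adherence". The visit descriptions in 7.3 to 7.6 include a weight check at each of those visits.

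**The analysis uses counts.** SAP 7.9.9.1 states: "Percent compliance will be calculated from total number of applications and total number of expected applications as follows". The numerator is the number of diary entries, and no weight enters. Amount appears only in the list of exposure summaries, which ends with "percent compliance, and total amount of study drug applied". Protocol 11.3.3 also frames compliance as applications made or missed, and 11.3.4 asks only for amount by weight and number of days. The gap therefore lies between 8.5 on one side and both 11.3.3 and the SAP on the other.

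**The treated area changes at Day 15.** Until the Day 15 samples are taken, the baseline area is treated even where it has cleared. After that, "the study drug will only be applied to the involved areas" (SAP 4.1).

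**The concern.** The primary objective is systemic exposure under maximal-use conditions. Protocol 6.9.2 keeps cleared skin under treatment up to the Day 15 samples for that reason. Whether the condition was met depends on grams applied, and no planned table compares grams applied with grams prescribed.

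No other part of the analysis fills the gap. Protocol section 9 counts a dosing error as a violation, but SAP 7.9.4 says deviations are neither entered nor summarized. SAP 7.9.7 takes every safety-population subject with PK data and sets no adherence condition. The PK listings hold concentrations and parameters, not dose.

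A reader of the report who sees low Day 15 concentrations would want to know whether they reflect low absorption or too little ointment in the preceding two weeks. The planned tables could show compliance near 100% in either case. With about 8 children in each of the two younger groups (SAP 4.1.2), a few under-dosed children could shift a group summary.

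**Working it through.** **1. The plan's own example (Protocol 8.3).** 0.7 m² × 0.32 × 10 g/m² = 2.24 g per application; × 2 = 4.48 g per day; × 7 = 31.36 g per week; ÷ 27 g = 1.16 tubes. All four figures match the protocol.

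**2. Expected applications (SAP 7.9.9.1).** The formula is 2 × (completion date − first application date), capped at 58. Completion on Day 28, 29 or 30 gives 54, 56 or 58. The rest of this check uses Day 29, so 56.

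**3. Response of the compliance score to under-application.** Take 0.7 m² and 35% BSA, with the prescribed amount held constant and all 56 applications recorded. The prescribed dose is 0.7 × 0.35 × 10 = 2.45 g, or 137.2 g over 56 applications. The fractions applied are assumptions.

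| Fraction of each dose applied | Total grams | SAP compliance | Grams applied / prescribed |
|---|---|---|---|
| 100% | 137.2 | 100% | 100% |
| 75% | 102.9 | 100% | 75% |
| 50% | 68.6 | 100% | 50% |
| 25% | 34.3 | 100% | 25% |

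Counting by visit, as 11.3.3 asks, would not change the third column.

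**4. Whether total grams can stand in.** It cannot, because prescriptions differ between children.
- 0.5 m², 35%, full dose: 1.75 g × 56 = 98 g.
- 1.0 m², 35%, half dose: 3.5 g × 0.5 × 56 = 98 g.

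The two children have the same total and the same 100% score, but one received half the prescription. At the minimum involvement for each age, with the BSA values in Protocol 6.7, prescribed grams run from 1.75 g (0.5 m², 35%) to 4.0 g (1.6 m², 25%) or 4.2 g (1.2 m², 35%). The ratios are 4.0/1.75 = 2.3 and 4.2/1.75 = 2.4.

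The total also adds two phases. The 56 applications are 28 on Days 1 to 14, the Day 15 clinic dose, and 27 afterwards. For 1.6 m² with 40% treated to Day 15 (assumed), the dose is 6.4 g and 29 applications make 185.6 g. The mean per application over 56 then depends on the area treated later (also assumed):
- 15%: (185.6 + 2.4 × 27)/56 = 250.4/56 = 4.47 g, 70% of 6.4 g.
- 30%: (185.6 + 4.8 × 27)/56 = 315.2/56 = 5.63 g, 88%.
- 40%: 100%.

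A low total can therefore come from improvement as well as from under-dosing.

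**5. Reach into the Day 15 PK.** Let R be the share of Day 15 exposure that comes from doses before the clinic dose, and f the fraction applied at those doses. If exposure is proportional to amount, doses add, and the clinic dose is full, relative exposure is R × f + (1 − R). With f = 0.6 the loss is 0.4 × R, between 0% and 40%. The documents give no value for R. The full 40% loss would need the same shortfall at every dose, including the observed one.

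**6. Where the weighing falls.** In the Schedule of Activities, the V4 compliance check is marked as done before dosing. Tube weights from V2 to V4 therefore cover about 28 applications, and the Day 15 clinic dose falls in the V4 to V6 interval. In the 15% example, a fully adherent child would show 6.4 + 64.8 = 71.2 g in that interval. Set against 28 × 2.4 = 67.2 g, this is 106%.

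**The case against.** **The PK-day doses are observed.** Day 1 and Day 15 doses are applied in clinic, the Schedule of Activities lists observation of dose application at those visits, and Appendix A tells families that staff will watch. This stands. Home under-dosing cannot affect the Day 1 profile, and it reaches Day 15 mainly through the pre-dose level and accumulation.

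**Under-dosing is controlled during conduct.** Families have a scale and an acceptable dosing range, an adult verifies each weighing, and sites check tube weights at V3 to V6. These controls may well catch a problem, and they serve the adherence purpose in 8.5, which does not promise a gram-based statistic. They leave nothing in the tables, however. Protocol section 9 lets the sponsor decide whether a violation leads to data being censored, but the SAP has no rule for this.

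**The SAP follows the protocol's statistical section.** This is correct: 11.3.3 counts applications and 11.3.4 asks for amount. The study is descriptive and its sample size is not based on inference. The point is therefore a useful addition, and the planned analysis is not broken without it.

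**The data remain available.** Tube weights and diary amounts are collected, so the ratio could be computed later. That is so, but specifying it in advance settles the source of grams, the intervals and the handling of discarded ointment before results are seen.

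**A stronger reading to avoid.** A reader might infer that the four-week total misstates the dose behind the PK profiles. The documents do not support that. The total sits under Extent of Exposure in the safety analyses, where cumulative grams is a legitimate measure, and nothing presents it as the PK-day dose.

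**Conclusion.** The concern holds as a gap in reporting. Under the stated rule, a child who records every application scores 100% whatever fraction of the prescribed grams is applied. Total grams cannot correct this, because prescriptions differ about 2.3- to 2.4-fold even at minimum involvement and the total combines two phases. The tables therefore cannot show whether maximal-use dosing was delivered in the two weeks before the Day 15 samples.

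The effect on the primary results is not known. The documents give no rate of under-dosing and no basis for proportionality. A reader might infer that a 40% shortfall means a 40% loss of Day 15 exposure, but that is an upper illustration which needs the shortfall at every dose, the observed one included, and proportionality as well. The phase-mixing figures in the working (70% to 100%) rest on assumed areas. The 98 g example assumes a constant prescription and all 56 applications recorded.

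The change should be made because it is cheap and bears on the condition that defines the primary objective.

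**What to change.** Keep the application count and add to SAP 7.9.9.1, for each subject:

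100 × grams applied / (prescribed grams per application × expected applications)

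- **Intervals.** Report it for the maximal-use phase, from Day 1 to the V4 pre-dose weighing (about 28 applications), and separately for the later phase. Take the Day 15 clinic dose out of the later interval and report it on its own.
- **Denominator.** Use the prescribed grams in force at each application, updated when the treated area changes, from the inputs in the eCRF dosing module.
- **Source of grams.** Use diary grams applied as the main source and tube weights as a cross-check. State that tube weights include ointment that families discard under Appendix A unless the discard chart is entered.
- **PK listing.** Show prescribed and recorded grams for the Day 1 and Day 15 clinic applications beside each child's Cmax and AUC0-last.
- **Consistency.** Align Protocol 11.3.3 with 8.5, or note the added measure in SAP section 5.

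The cost is SAP wording, a little extra programming for one table and a few listing columns, and possibly entry of the discard chart, which the protocol does not say is in the eCRF. Reported compliance may look less favourable.
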